10.2. Appendix 2: Clinical Laboratory Tests

The following safety laboratory tests will be performed at times defined in the [SoA](#) section of this protocol. Additional laboratory results may be reported on these samples as a result of the method of analysis or the type of analyzer used by the clinical laboratory, or as derived from calculated values. These additional tests would not require additional collection of blood. Unscheduled clinical laboratory measurements may be obtained at any time during the study to assess any perceived safety issues.

Table 2. Protocol-Required Safety Laboratory Assessments

Hematology	Chemistry	Urinalysis	Other
Hemoglobin	BUN and creatinine	pH	
Pregnancy test (β-hCG)^c
Hematocrit	Glucose	Glucose (qual)	At screening only:
RBC count	Calcium	Protein (qual)	
FSH^bUrine drug screeningHepatitis B surface antigenHepatitis C antibodyHIV
MCV	Sodium	Blood (qual)	
MCH	Potassium	Ketones	
MCHC	Chloride	Nitrites	
Platelet count	Total	Leukocyte esterase	
WBC count	CO_2 (bicarbonate)	Urobilinogen	
Total neutrophils (Abs)	AST,	Urine bilirubin	
Eosinophils (Abs)	ALT	Microscopy ^a	
Monocytes (Abs)	Total bilirubin		
Basophils (Abs)	Alkaline phosphatase		
Lymphocytes (Abs)	Uric acid		
	CRP		
	Pre-albumin		
	Albumin		
	Total protein		

- a. Only if urine dipstick is positive for blood, protein, nitrites, or leukocyte esterase.
- b. For confirmation of postmenopausal status only.
- c. Local urine testing will be standard for the protocol unless serum testing is required by local regulation or IRB/EC. Serum or urine β -hCG for female participants of childbearing potential.

Investigators must document their review of each laboratory safety report.

10.3. Appendix 3: Adverse Events: Definitions and Procedures for Recording, Evaluating, Follow-up, and Reporting

10.3.1. Definition of AE

AE Definition

• An AE is any untoward medical occurrence in a patient or clinical study participant, temporally associated with the use of study intervention, whether or not considered related to the study intervention.• NOTE: An AE can therefore be any unfavorable and unintended sign (including an abnormal laboratory finding), symptom, or disease (new or exacerbated) temporally associated with the use of study intervention.

Events Meeting the AE Definition

• Any abnormal laboratory test results (hematology, clinical chemistry, or urinalysis) or other safety assessments (eg, ECG, radiological scans, vital sign measurements), including those that worsen from baseline, considered clinically significant in the medical and scientific judgment of the investigator. Any abnormal laboratory test results that meet any of the conditions below must be recorded as an AE:
• Is associated with accompanying symptoms.• Requires additional diagnostic testing or medical/surgical intervention.• Leads to a change in study dosing (outside of any protocol-specified dose adjustments) or discontinuation from the study, significant additional concomitant drug treatment, or other therapy.• Exacerbation of a chronic or intermittent preexisting condition including either an increase in frequency and/or intensity of the condition.• New conditions detected or diagnosed after study intervention administration even though it may have been present before the start of the study.• Signs, symptoms, or the clinical sequelae of a suspected drug-drug interaction.• Signs, symptoms, or the clinical sequelae of a suspected overdose of either study intervention or a concomitant medication. Overdose per se will not be reported as an AE/SAE unless it is an intentional overdose taken with possible suicidal/self-harming intent. Such overdoses should be reported regardless of sequelae.

Events NOT Meeting the AE Definition

- Any clinically significant abnormal laboratory findings or other abnormal safety assessments which are associated with the underlying disease, unless judged by the investigator to be more severe than expected for the participant's condition.
- The disease/disorder being studied or expected progression, signs, or symptoms of the disease/disorder being studied, unless more severe than expected for the participant's condition.
- Medical or surgical procedure (eg, endoscopy, appendectomy): the condition that leads to the procedure is the AE.
- Situations in which an untoward medical occurrence did not occur (social and/or convenience admission to a hospital).
- Anticipated day-to-day fluctuations of preexisting disease(s) or condition(s) present or detected at the start of the study that do not worsen.
- Worsening of signs and symptoms of the malignancy under study should be recorded as AEs in the appropriate section of the CRF. Disease progression assessed by measurement of malignant lesions on radiographs or other methods should not be reported as AEs.

10.3.2. Definition of SAE

If an event is not an AE per definition above, then it cannot be an SAE even if serious conditions are met (eg, hospitalization for signs/symptoms of the disease under study, death due to progression of disease).

An SAE is defined as any untoward medical occurrence that, at any dose:
a. Results in death
b. Is life-threatening
The term "life-threatening" in the definition of "serious" refers to an event in which the participant was at risk of death at the time of the event. It does not refer to an event that hypothetically might have caused death if it were more severe.
c. Requires inpatient hospitalization or prolongation of existing hospitalization
In general, hospitalization signifies that the participant has been detained (usually involving at least an overnight stay) at the hospital or emergency ward for observation

and/or treatment that would not have been appropriate in the physician's office or outpatient setting. Complications that occur during hospitalization are AEs. If a complication prolongs hospitalization or fulfills any other serious criteria, the event is serious. When in doubt as to whether "hospitalization" occurred or was necessary, the AE should be considered serious.

Hospitalization for elective treatment of a preexisting condition that did not worsen from baseline is not considered an AE.

d. Results in persistent disability/incapacity

- The term disability means a substantial disruption of a person's ability to conduct normal life functions.
- This definition is not intended to include experiences of relatively minor medical significance such as uncomplicated headache, nausea, vomiting, diarrhea, influenza, and accidental trauma (eg, sprained ankle) which may interfere with or prevent everyday life functions but do not constitute a substantial disruption.

e. Is a congenital anomaly/birth defect

f. Other situations

- Medical or scientific judgment should be exercised in deciding whether SAE reporting is appropriate in other situations such as important medical events that may not be immediately life-threatening or result in death or hospitalization but may jeopardize the participant or may require medical or surgical intervention to prevent one of the other outcomes listed in the above definition. These events should usually be considered serious.
- Examples of such events include invasive or malignant cancers, intensive treatment in an emergency room or at home for allergic bronchospasm, blood dyscrasias or convulsions that do not result in hospitalization, or development of drug dependency or drug abuse.
- Progression of the malignancy under study (including signs and symptoms of progression) should not be reported as an SAE unless the outcome is fatal within the active collection period. Hospitalization due to signs and symptoms of disease progression should not be reported as an SAE. If the malignancy has a fatal outcome during the study or within the active collection period, then the event leading to death must be recorded as an AE on the CRF, and as an SAE with CTCAE Grade 5 (see the [Assessment of Intensity](#) section).
- Suspected transmission via a Pfizer product of an infectious agent, pathogenic or non-pathogenic, is considered serious. The event may be suspected from clinical symptoms or laboratory findings indicating an infection in a patient exposed to a

Pfizer product. The terms “suspected transmission” and “transmission” are considered synonymous. These cases are considered unexpected and handled as serious expedited cases by pharmacovigilance personnel. Such cases are also considered for reporting as product defects, if appropriate.

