2.3.1. Risk Assessment

Potential Risk of Clinical Significance	Summary of Data/Rationale for Risk	Mitigation Strategy
Study Intervention(s) PF-06946860		
Potential risks associated with PF-06946860 include the following: 
1. Injection site reactions.2. This will be the first administration of PF-06946860 to patients with a variety of cancer types and that may be receiving a variety of anti-tumor therapies. Therefore, this will be the first clinical experience to assess safety in this context.	Single doses of PF-06946860 were well-tolerated by study participants when administered subcutaneously at 0.1 to 300 mg in 2 completed Phase 1 studies. All AEs reported across the 2 completed studies were mild. The risk of injection site reaction is not anticipated to be elevated beyond that expected with any subcutaneously administered treatment.	Eligibility criteria have been selected to ensure that only appropriate participants, who are not at apparent increased risk, are included in the study (see Section 5). Adverse events and clinical laboratory results will be monitored on an ongoing basis. Injection site reactions will be monitored, and injection sites rotated.
Use of a placebo arm.	Use of a placebo arm represents a risk of lack of benefit for those not receiving active therapy. As there are no data on efficacy yet, this risk cannot be assessed.	As the endpoint under evaluation (appetite) is anticipated to change rapidly, the study has been designed with a short duration (6 weeks), and with the potential for participation in an optional OLT Part B where all participants would receive PF-06946860. The study has also been designed with, a 2:1 randomization ratio, in order to increase participants' chances of receiving active therapy.

PFIZER CONFIDENTIAL

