8.3.7. Disease-Related Events and/or Disease-Related Outcomes Not Qualifying as AEs or SAEs

Not applicable.

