The investigator will make an assessment of intensity for each AE and SAE reported during the study and assign it to 1 of the following categories:

GRADE	Clinical Description of Severity
1	MILD adverse event
2	MODERATE adverse event
3	SEVERE adverse event
4	LIFE-THREATENING consequences; urgent intervention indicated
5	DEATH RELATED TO adverse event

An event is defined as "serious" when it meets at least 1 of the predefined outcomes as described in the definition of an SAE, NOT when it is rated as severe.

Assessment of Causality

- The investigator is obligated to assess the relationship between study intervention and each occurrence of each AE/SAE.
- A "reasonable possibility" of a relationship conveys that there are facts, evidence, and/or arguments to suggest a causal relationship, rather than a relationship cannot be ruled out.
- The investigator will use clinical judgment to determine the relationship.

- Alternative causes, such as underlying disease(s), concomitant therapy, and other risk factors, as well as the temporal relationship of the event to study intervention administration, will be considered and investigated.
- The investigator will also consult the IB and/or product information, for marketed products, in his/her assessment.
- For each AE/SAE, the investigator **must** document in the medical notes that he/she has reviewed the AE/SAE and has provided an assessment of causality.
- There may be situations in which an SAE has occurred, and the investigator has minimal information to include in the initial report to the sponsor. However, **it is very important that the investigator always make an assessment of causality for every event before the initial transmission of the SAE data to the sponsor.**
- The investigator may change his/her opinion of causality in light of follow-up information and send an SAE follow-up report with the updated causality assessment.
- The causality assessment is one of the criteria used when determining regulatory reporting requirements.

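### Protocol 10.3.2 keeps non-fatal admissions for progression symptoms out of SAE reporting without the severity condition in 10.3.1, so the same admission is an SAE under one rule and not under another

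*Protocol*

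**What the plan says.** Four parts of the protocol bear on a participant admitted to hospital, and not dying, because of progression symptoms.

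- **Section 10.3.1, events not meeting the AE definition.** The exclusion covers "expected progression, signs, or symptoms of the disease/disorder being studied, unless more severe than expected for the" participant's condition. The last bullet of the same list asks sites to record worsening signs and symptoms of the malignancy as AEs. Only progression assessed by measuring lesions is kept out.
- **Section 10.3.2, opening and criterion (c).** An event that is not an AE cannot be an SAE, even if a seriousness condition is met. Otherwise, one of the listed outcomes makes an event an SAE, and criterion (c) reads "Requires inpatient hospitalization or prolongation of existing hospitalization".
- **Section 10.3.2, later bullet on the malignancy under study.** Progression, including its signs and symptoms, "should not be reported as an SAE unless the outcome is fatal within the active collection period". The next sentence is "Hospitalization due to signs and symptoms of disease progression should not be reported as an SAE". A fatal malignancy outcome is to be recorded as an AE and as a Grade 5 SAE.
- **Sections 8.3.1.1 and 10.3.3.** All SAEs go to the sponsor's safety group within 24 hours of awareness. The 10.3.3 table has all nonserious AEs recorded on the CRF and none sent on the SAE form.

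Section 8.3.7, titled "Disease-Related Events and/or Disease-Related Outcomes Not Qualifying as AEs or SAEs", is marked as not applicable.

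**The concern.** The bullet on the malignancy does not repeat the severity condition that 10.3.1 uses to separate expected disease symptoms from AEs. An investigator who admits a participant for progression symptoms clearly worse than expected can be led to two different answers by one appendix.

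The stake is classification and speed. If the bullet is followed, the sponsor's safety group does not receive the event as an SAE within 24 hours, and the event enters the Part A summaries as nonserious. AE incidence in Part A is a secondary endpoint, there is no DMC or internal review committee (Section 9.6), and the risk assessment in Section 2.3.1 says of this patient group that "this will be the first clinical experience to assess safety in this context". The situation is foreseeable in advanced cancer: Section 7.1 lists both progression and hospitalization among the reasons for stopping study intervention.

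**Working it through.** The plan has no figure to reproduce. The check follows one case through the text: a non-fatal inpatient admission for progression symptoms that the investigator judges worse than expected for that participant.

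**Route A: 10.3.1, then the opening of 10.3.2, then criterion (c)**

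1. Is it an AE? The 10.3.1 exclusion is lifted once symptoms are worse than expected. The last bullet of that list points the same way, although it sits under a heading for events that are not AEs. Answer: yes.
2. Does the opening of 10.3.2 bar SAE status? It does so only for events that are not AEs. Answer: no.
3. Is a seriousness outcome met? Criterion (c), inpatient hospitalization. Answer: yes.
4. Result: an SAE, due at the sponsor's safety group within 24 hours (8.3.1.1).

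**Route B: the later bullet in 10.3.2**

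1. Is the admission due to signs and symptoms of progression? Yes.
2. Was the outcome fatal within the active collection period? No.
3. Does the bullet ask about severity relative to expectation? No.
4. Result: not reported as an SAE. The event is recorded on the CRF as an AE, and the nonserious row of the 10.3.3 table sends nothing to the safety group.

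The routes agree when symptoms are as expected and the participant survives. They differ only for non-fatal admissions with worse-than-expected symptoms, and that is the whole extent of the conflict.

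Section 10.3.3 does not settle it. It calls an event serious "when it meets at least 1 of the predefined outcomes as described in the definition of an SAE", and that definition contains both criterion (c) and the bullet.

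The two ends of 10.3.2 also fit poorly on deaths. The opening gives death from progression as an example of an event that may fail to be an SAE because it is not an AE; the later bullet requires a fatal malignancy outcome to be recorded as an SAE. This suggests that the two were not written against each other.

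**Leverage of one event.** Inputs: 27 active and 13 placebo participants planned (Section 9.2). If all are dosed, and one participant's only SAE is such an admission, that arm's Part A SAE incidence changes by

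- active: 1/27 = 3.7 percentage points;
- placebo: 1/13 = 7.7 percentage points.

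This shows how sensitive the summary is to one classification. It does not estimate how often the situation will arise.

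**The case against.** The strongest reply is that the two sets of rules answer different questions. Section 10.3.1 decides whether something is an AE; the bullet decides whether a progression event goes on an SAE form. On that reading the bullet is a specific rule that overrides criterion (c), and a site can follow everything by recording the symptom as an AE and filing no SAE form. This is a possible reading, but the protocol does not say that it governs, and the opening of 10.3.2 ties exclusion to the event not being an AE. If the override was intended, the consequence remains: unexpectedly severe admissions leave the SAE count and 24-hour reporting.

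There are real safeguards. These events stay on the CRF with a CTCAE grade and enter the AE summaries. Section 8 asks for safety issues to be discussed with the sponsor immediately. The sponsor is unblinded in Part A and may review the data during the study (Sections 6.3.2 and 9.5). Participants and investigators are blinded, so inconsistent classification has no evident reason to favor one arm. These points limit the harm; they do not restore the serious classification.

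A reader might also infer more than the text supports:

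- *That drug-related admissions are exempted.* The bullet covers only admissions due to progression, so one attributed to study drug falls outside it. Section 10.3.3 requires a causality assessment for every event and treats unknown causality as related for reporting.
- *That marking 8.3.7 not applicable means no disease-related event is exempt.* The neighboring Section 8.3.6, on cardiovascular and death events, is marked the same way, yet fatal events are plainly reportable.
- *That the bullet has no exception at all.* It excepts fatal outcomes.
- *That the SAE rate is understated by a known amount.* The documents give no rate for these admissions. The SAP plans only descriptive safety summaries, with no confidence bound on SAE incidence.

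**Conclusion.** The conflict is real and narrow. One type of event, a non-fatal admission for progression symptoms worse than expected, is an SAE under 10.3.1, the opening of 10.3.2 and criterion (c), and is not an SAE under the later bullet in 10.3.2. Under the bullet the event is still recorded as an AE; what it loses is its seriousness and its 24-hour report.

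The number of participants affected cannot be derived from the documents. In arms this small, a single case is visible in the SAE summary. That statement assumes that the sponsor's reporting standards, which SAP 6.6.1 relies on but does not reproduce, include SAE incidence by arm. The primary appetite analysis is not touched. The point should be settled in the next amendment because it concerns how quickly serious events reach the sponsor.

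**What to change.** Reconcile Sections 10.3.1 and 10.3.2 by carrying the condition that 10.3.1 already contains into the 10.3.2 bullet. The rule would then be that admission for signs and symptoms of progression is not reported as an SAE, except where these are worse than would be expected for that participant. The existing treatment of fatal outcomes can stay. Replace the entry in Section 8.3.7 with a cross-reference to this rule, so that a reader of the main text can find it.

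The cost is a sentence in Appendix 3, a line in 8.3.7, a short clarification to sites, and a few more SAE report forms. No SAP change is needed. A separate count of all hospitalizations by arm would go further than the defect requires, and it could need CRF data that the documents do not show to be collected for nonserious events.

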10.3.3. Recording/Reporting and Follow-up of AEs and/or SAEs

AE and SAE Recording/Reporting

The table below summarizes the requirements for recording adverse events on the CRF and for reporting serious adverse events on the CT SAE Report Form to Pfizer Safety. These requirements are delineated for 3 types of events: (1) SAEs; (2) nonserious adverse events (AEs); and (3) exposure to the study intervention under study during pregnancy or breastfeeding, and occupational exposure.

It should be noted that the CT SAE Report Form for reporting of SAE information is not the same as the AE page of the CRF. When the same data are collected, the forms must be completed in a consistent manner. AEs should be recorded using concise medical terminology and the same AE term should be used on both the CRF and the CT SAE Report Form for reporting of SAE information.

Safety Event	Recorded on the CRF	Reported on the CT SAE Report Form to Pfizer Safety Within 24 Hours of Awareness
SAE	All	All
Nonserious AE	All	None
Exposure to the study intervention under study during pregnancy or breastfeeding, and occupational exposure	All AEs/SAEs associated with exposure during pregnancy or breastfeeding. Occupational exposure is not recorded.	All (and EDP supplemental form for EDP) Note: Include all SAEs associated with exposure during pregnancy or breastfeeding. Include all AEs/SAEs associated with occupational exposure.

- When an AE/SAE occurs, it is the responsibility of the investigator to review all documentation (eg, hospital progress notes, laboratory reports, and diagnostic reports) related to the event.
- The investigator will then record all relevant AE/SAE information in the CRF.

- It is **not** acceptable for the investigator to send photocopies of the participant's medical records to Pfizer Safety in lieu of completion of the CT SAE Report Form/AE/SAE CRF page.
- There may be instances when copies of medical records for certain cases are requested by Pfizer Safety. In this case, all participant identifiers, with the exception of the participant number, will be redacted on the copies of the medical records before submission to Pfizer Safety.
- The investigator will attempt to establish a diagnosis of the event based on signs, symptoms, and/or other clinical information. Whenever possible, the diagnosis (not the individual signs/symptoms) will be documented as the AE/SAE.

Assessment of Intensity

The investigator will make an assessment of intensity for each AE and SAE reported during the study and assign it to 1 of the following categories:

GRADE	Clinical Description of Severity
1	MILD adverse event
2	MODERATE adverse event
3	SEVERE adverse event
4	LIFE-THREATENING consequences; urgent intervention indicated
5	DEATH RELATED TO adverse event

An event is defined as "serious" when it meets at least 1 of the predefined outcomes as described in the definition of an SAE, NOT when it is rated as severe.

Assessment of Causality

- The investigator is obligated to assess the relationship between study intervention and each occurrence of each AE/SAE.
- A "reasonable possibility" of a relationship conveys that there are facts, evidence, and/or arguments to suggest a causal relationship, rather than a relationship cannot be ruled out.
- The investigator will use clinical judgment to determine the relationship.

- Alternative causes, such as underlying disease(s), concomitant therapy, and other risk factors, as well as the temporal relationship of the event to study intervention administration, will be considered and investigated.
- The investigator will also consult the IB and/or product information, for marketed products, in his/her assessment.
- For each AE/SAE, the investigator **must** document in the medical notes that he/she has reviewed the AE/SAE and has provided an assessment of causality.
- There may be situations in which an SAE has occurred, and the investigator has minimal information to include in the initial report to the sponsor. However, **it is very important that the investigator always make an assessment of causality for every event before the initial transmission of the SAE data to the sponsor.**
- The investigator may change his/her opinion of causality in light of follow-up information and send an SAE follow-up report with the updated causality assessment.
- The causality assessment is one of the criteria used when determining regulatory reporting requirements.
- If the investigator does not know whether or not the study intervention caused the event, then the event will be handled as “related to study intervention” for reporting purposes, as defined by the sponsor. In addition, if the investigator determines that an SAE is associated with study procedures, the investigator must record this causal relationship in the source documents and CRF, and report such an assessment in the dedicated section of the CT SAE Report Form and in accordance with the SAE reporting requirements.

Follow-up of AEs and SAEs

- The investigator is obligated to perform or arrange for the conduct of supplemental measurements and/or evaluations as medically indicated or as requested by the sponsor to elucidate the nature and/or causality of the AE or SAE as fully as possible. This may include additional laboratory tests or investigations, histopathological examinations, or consultation with other healthcare providers.
- If a participant dies during participation in the study or during a recognized follow-up period, the investigator will provide Pfizer Safety with a copy of any postmortem findings including histopathology.
- New or updated information will be recorded in the originally completed CRF.

- The investigator will submit any updated SAE data to the sponsor within 24 hours of receipt of the information.

